## Protocol Amendment Summary of Changes

### Protocol History

Version Number	Type	Version Date
1.0	Original Protocol	05 Apr 2022
2.0	Global Amendment to the Original Protocol	27 Jul 2022
3.0	Global Amendment to Protocol Version 2.0	02 Nov 2022

### Protocol Version 3.0 (02 November 2022)

#### Overall Rationale for the Amendment

The overall rationale for this amendment was to address minor comments from the regulatory authority and ethics committees.

The following elements of the protocol were revised:

Section # and Name	Description of Change	Brief Rationale
Section 1.3 Schedule of Activities (Table 1) Section 2.3.1 Risk Assessment Section 5.2 Exclusion Criteria	A COVID-19 antigen test was added to the SoA and it was clarified that only patients with a negative COVID-19 antigen test at screening are eligible.	To clarify that COVID-19 antigen tests will be performed at screening and as needed as requested by the regulatory authority.
CCI [REDACTED]	[REDACTED] [REDACTED] [REDACTED] [REDACTED] [REDACTED]	[REDACTED] [REDACTED] [REDACTED]
Section 6.6 Continued Access to Study Intervention after the End of the Study	Rescue treatment will not be provided by the Sponsor, but locally available medications will be used as specified in Section 6.8.1.	To correct an error.
Section 8.4 Pharmacokinetics CCI [REDACTED]	Blood sample volumes were removed.	To clarify that blood volumes will be specified in the laboratory manual.
Appendix 2 Study Governance (Informed Consent Process)	Participants who are rescreened will be required to sign a new ICF if the rescreening occurs later than 7 days after the initial screening visit.	To correct an error.
Throughout	Minor editorial and document formatting revisions	Minor; therefore, have not been summarized.

- Confidential -

This document is the property of Merck KGaA, Darmstadt, Germany, or one of its subsidiaries. It is intended for restricted use only and may not – in full or part – be passed on, reproduced, published or used without express permission of Merck KGaA, Darmstadt, Germany, or its subsidiary. Copyright © 2022 by Merck KGaA, Darmstadt, Germany, or its subsidiary. All rights reserved.

## 1 Protocol Summary

### 1.1 Synopsis

**Protocol Title:** Phase IIa Proof of Concept, Multicenter, Randomized, Open-label Study to Evaluate the Safety, Efficacy, and Pharmacokinetics of the Combination M5717 plus Pyronaridine Administered once Daily for 1 or 2 Days to Adults and Adolescents with Acute Uncomplicated *Plasmodium falciparum* Malaria

**Short Title:** Phase IIa Proof of Concept Study of M5717-Pyronaridine in Adults and Adolescents with acute uncomplicated *Plasmodium falciparum* Malaria

**Rationale:** Artemisinin-based combination therapies (ACTs) have been the gold standard for acute uncomplicated *P. falciparum* malaria, but the increasing reports of emergent resistant strains to artemisinin-related compound therapies makes it necessary to look for new therapeutic tools. In this context, the current study intends to explore in a Proof of Concept the safety, preliminary efficacy, and pharmacokinetics (PK) of M5717 (free base) in combination with pyronaridine (tetraphosphate). An ACT containing combination pyronaridine-artesunate (Pyramax) will be used as internal control, mainly for safety purposes.

### Objectives and Endpoints/Estimands:

#### Part A – Safety/PK Run-in

Objectives	Estimands/Endpoints	Ref. #
Primary		
To evaluate the safety and tolerability of the M5717-pyronaridine combination in adult participants with acute uncomplicated malaria due to P. falciparum	
Endpoint: Incidence, severity, and seriousness of study intervention-related treatment-emergent adverse events (TEAEs), as per Common Terminology Criteria for Adverse Events (CTCAE) v 5.0
 
Additional endpoints related to safety and tolerability up to Day 29 (<math>\pm 2</math> days): laboratory assessments, electrocardiograms (ECGs), and vital signs.
	1
Secondary		
To characterize the PK of M5717 and pyronaridine in adult participants with acute uncomplicated malaria due to P. falciparum	
Endpoint:
 
 
PK profiles for M5717 and pyronaridine
 
PK parameters of M5717 and pyronaridine such as <math>AUC_{0-\text{last}}</math>, <math>AUC_{0-\infty}</math>, <math>AUC_{0-24}</math>, <math>C_{\max}</math>, <math>t_{\frac{1}{2}}</math>, <math>t_{\max}</math>, <math>CL/F</math>, <math>V_z/F</math>, when data permits
 
	2
To describe the clinical efficacy of the M5717-pyronaridine combination in adult participants with acute uncomplicated malaria due to P. falciparum	
Endpoint: Early treatment failure (ETF) defined as meeting any of the following:
 
 
Danger signs or severe malaria 1, 2, or 3 days after treatment, in the presence of parasitemia
 
Parasitemia 2 days after treatment higher than on day of treatment, irrespective of axillary temperature
 
Parasitemia 3 days after treatment with axillary temperature <math>\geq 37.5^{\circ}\text{C}</math>
 
Parasitemia 3 days after treatment <math>\geq 25\%</math> of count on day of treatment
 
 
Target Population: Adult patients with acute uncomplicated malaria due to P. falciparum
 
Treatment: Single dose M5717 330 mg plus pyronaridine 360 mg
	3

Objectives	Estimands/Endpoints	Ref. #
	
Intercurrent Event Strategy:
 
 
Intake of rescue medication before or at Day 4: Composite variable strategy, i.e., endpoint is considered as failure (= presence of ETF)
 
Intake of prohibited medication that impacts treatment effect (e.g., drug with antimalarial activity) before or at Day 4: Principal Stratum strategy, i.e., treatment effect is estimated within the principal stratum of participants that potentially don't experience the intercurrent event (ICE)
 
Experience of any event that affects absorption (i.e., vomiting within the study intervention absorptive period of <math>2 \times</math> median <math>t_{max}</math>) or immune response (severe immunocompromised participants): Treatment policy strategy, i.e., treatment effect is estimated regardless of intercurrent event or Principal Stratum strategy
 
Premature study discontinuation before or at Day 4 due to lack of efficacy: Composite variable strategy
 
Death due to malaria before or at Day 4: Composite variable strategy
 
 
Population-level Summary: ETF rate, i.e., proportion of participants with ETF.
	
	
Endpoint: Late clinical failure (LCF) defined as:
 
 
Danger signs or severe malaria in the presence of parasitemia on any day between 4 and 28 days after treatment (i.e., between Days 5 and 29) in participants who did not previously meet any of the criteria of ETF
 
Presence of parasitemia on any day between 4 and 28 days after treatment with axillary temperature <math>\geq 37.5^{\circ}\text{C}</math> in participants who did not previously meet any of the criteria of ETF
 
 
Target Population: See endpoint 3
 
Treatment: See endpoint 3
 
Intercurrent Event Strategy:
 
 
Intake of rescue medication between 4 and 28 days after treatment: Composite variable strategy, i.e., endpoint is considered as failure (= presence of LCF)
 
Intake of prohibited medication that impacts treatment effect (e.g., drug with antimalarial activity) between 4 and 28 days after treatment: Principal Stratum strategy, i.e., treatment effect is estimated within the principal stratum of participants that potentially don't experience the ICE
 
Experience of any event that affects absorption (i.e., vomiting within the study intervention absorptive period of <math>2 \times</math> median <math>t_{max}</math>) or immune response (severe immunocompromised participants): Treatment policy strategy, i.e., treatment effect is estimated regardless of intercurrent event or Principal Stratum strategy
 
Premature study discontinuation between 4 and 28 days after treatment due to lack of efficacy: Composite variable strategy
 
Death due to malaria between 4 and 28 days after treatment: Composite variable strategy
 
 
Population-level Summary: LCF rate, i.e., proportion of participants with LCF
	4

Objectives	Estimands/Endpoints	Ref. #
	
Endpoint: Late parasitological failure (LPF) defined as: Presence of parasitemia on any day between 7 and 28 days after treatment (i.e., between Days 8 and 29) with axillary temperature <math>< 37.5^{\circ}\text{C}</math> in participants who did not previously meet any of the criteria of ETF or LCF
 
Target Population: See endpoint 3
 
Treatment: See endpoint 3
 
Intercurrent Event Strategy:
 
 
• Intake of rescue medication between 7 and 28 days after treatment: Composite variable strategy, i.e., endpoint is considered as failure (= presence of LPF)
 
• Intake of prohibited medication that impacts treatment effect (e.g., drug with antimalarial activity) between 7 and 28 days after treatment: Principal Stratum strategy, i.e., treatment effect is estimated within the principal stratum of participants that potentially don't experience the ICE
 
• Experience of any event that affects absorption (i.e., vomiting within the study intervention absorptive period of <math>2 \times \text{median } t_{\text{max}}</math>) or immune response (severe immunocompromised participants): Treatment policy strategy, i.e., treatment effect is estimated regardless of intercurrent event or Principal Stratum strategy
 
• Premature study discontinuation between 7 and 28 days after treatment due to lack of efficacy: Composite variable strategy
 
• Death due to malaria between 7 and 28 days after treatment: Composite variable strategy
 
 
Population-level Summary: LPF rate, i.e., proportion of participants with LPF
	5
	
Endpoint: Crude (polymerase chain reaction [PCR]-uncorrected) Adequate Clinical and Parasitological Response (ACPR) 14, 28, and 42 days after treatment defined as absence of parasitemia (thick smear/microscopy), irrespective of axillary temperature, in participants who did not previously meet any of the criteria of ETF, LCF, or LPF
 
Target Population: See endpoint 3
 
Treatment: See endpoint 3
 
Intercurrent Event Strategy:
 
 
• Intake of rescue medication at any timepoint: Composite variable strategy, i.e., endpoint is considered as treatment failure
 
• Intake of prohibited medication that impacts treatment effect (e.g., drug with antimalarial activity) at any timepoint: Principal Stratum strategy, i.e., treatment effect is estimated within the principal stratum of participants that potentially don't experience the ICE
 
• Experience of any event that affects absorption (i.e., vomiting within the study intervention absorptive period of <math>2 \times \text{median } t_{\text{max}}</math>) or immune response (severe immunocompromised participants): Treatment policy strategy, i.e., treatment effect is estimated regardless of intercurrent event or Principal Stratum strategy
 
• Premature study discontinuation at any timepoint due to lack of efficacy: Composite variable strategy
 
• Death due to malaria at any timepoint: Composite variable strategy
 
 
Population-level Summary: Crude ACPR rate at each timepoint, i.e., proportion of participants with Crude ACPR at each timepoint
	6

Objectives	Estimands/Endpoints	Ref. #
	
Endpoint: PCR-adjusted ACPR 14, 28, and 42 days after treatment defined as absence of parasitemia (thick smear/microscopy, after adjustment for parasitemia due to new infections as determined by genotyping using PCR techniques), irrespective of axillary temperature, in participants who did not previously meet any of the criteria of ETF, LCF, or LPF.
 
Target Population: see endpoint 3
 
Treatment: see endpoint 3
 
Intercurrent Event Strategy: See endpoint 3
 
Population-level Summary: PCR-adjusted ACPR rate at each timepoint, i.e., proportion of participants with PCR-adjusted ACPR at each timepoint
	7
	
Endpoint: Crude (PCR-uncorrected) efficacy 8 days after treatment, defined as absence of parasitemia (thick smear/microscopy) in participants who did not previously meet any of the criteria of ETF or LCF
 
Target Population: See endpoint 3
 
Treatment: See endpoint 3
 
Intercurrent Event Strategy: See endpoint 3
 
Population-level Summary: Crude efficacy rate, i.e., proportion of participants with crude (PCR-uncorrected) efficacy 8 days after treatment (Day 9)
	8
	
Endpoint: PCR-adjusted efficacy 8 days after treatment as defined as absence of parasitemia (thick smear/microscopy, after adjustment for parasitemia due to new infections as determined by genotyping using PCR techniques) in participants who did not previously meet any of the criteria of ETF or LCF
 
Target Population: See endpoint 3
 
Treatment: See endpoint 3
 
Intercurrent Event Strategy: see endpoint 3
 
Population-level Summary: PCR-adjusted efficacy rate, i.e., proportion of participants with PCR-adjusted efficacy 8 days after treatment (Day 9)
	9
	
Endpoint: Parasite reduction rate (PRR) defined as decrease in viable parasites over 48 hours, corresponding to 1 asexual parasite life cycle
 
Target Population: See endpoint 3
 
Treatment: See endpoint 3
 
Intercurrent Event Strategy: see endpoint 3
 
Population-level Summary: Geometric mean of the PRR
	10
	
Endpoint: Fever clearance time defined as the time from first dosing to the first measurement of an axillary temperature <math>< 37.5^{\circ}\text{C}</math> for 2 consecutive temperature readings plus confirmed normal temperature 24 hours after the first normal body temperature reading
 
Target Population: Adult patients with acute uncomplicated malaria due to P. falciparum with an increased axillary temperature (<math>\geq 37.5^{\circ}\text{C}</math>)
 
Treatment: See endpoint 3
 
Intercurrent Event Strategy:
 
 
• Intake of rescue medication: Composite variable strategy, i.e., time to fever clearance is censored at Day 29
 
• Intake of concomitant medications as a continuous treatment that have an impact on fever: Composite variable strategy, i.e., time to fever clearance is censored at Day 29
 
	11

Objectives	Estimands/Endpoints	Ref. #
	
 
Intake of prohibited medication that impacts treatment effect (e.g., drug with antimalarial activity): Composite variable strategy, i.e., time to fever clearance is censored at Day 29
 
Experience of any event that affects absorption (i.e., vomiting within the study intervention absorptive period of <math>2 \times</math> median <math>t_{max}</math>) or immune response (severe immunocompromised participants): Treatment policy strategy, i.e., treatment effect is estimated regardless of intercurrent event or Principal Stratum strategy
 
Premature study discontinuation due to lack of efficacy: On-treatment strategy, i.e., time to fever clearance is censored at the day of the last available body temperature assessment
 
Death due to malaria: On-treatment strategy, i.e., time to fever clearance is censored at the day of the last available body temperature assessment
 
 
Population-level Summary: Median fever clearance time as estimated by Kaplan-Meier method
	
	
Endpoint: Parasite clearance time defined as time from dosing to the first negative (no parasites) film (microscopy)
 
Target Population: See endpoint 3
 
Treatment: See endpoint 3
 
Intercurrent Event Strategy: see previous endpoint with the exception of intake of concomitant medications, which is not an ICE for parasite clearance time. Censoring will be done at the day of the last available microscopy assessment.
 
Population-level Summary: Median parasite clearance time as estimated by Kaplan-Meier method
	12
	
Endpoint: Time to recrudescence, defined as the time from primary cure to the re-emergence of the same parasite strain that originated the primary infection
 
Target Population: Adult patients with acute uncomplicated malaria due to P. falciparum who are primarily cured
 
Treatment: See endpoint 3
 
Intercurrent Event Strategy: Intake of prohibited medication that impacts treatment effect (e.g., drug with antimalarial activity) at any timepoint: Principal Stratum strategy, i.e., treatment effect is estimated within the principal stratum of participants that potentially don't experience the ICE
 
Population-level Summary: Median time to recrudescence as estimated by Kaplan-Meier method
	13
	
Endpoint: Time to re-infection, defined as the time from primary cure to the re-emergence of a different parasite strain that originated the primary infection
 
Target Population: See endpoint 3
 
Treatment: See endpoint 3
 
Intercurrent Event Strategy: Intake of prohibited medication that impacts treatment effect (e.g., drug with antimalarial activity) at any timepoint: Principal Stratum strategy, i.e., treatment effect is estimated within the principal stratum of participants that potentially don't experience the ICE
 
Population-level Summary: Median time to re-infection as estimated by Kaplan-Meier method
	14

Objectives	Estimands/Endpoints	Ref. #
	
Endpoint: Time to re-emergence, defined as the time from primary cure to having recrudescence or re-infection (the first one that occurs)
 
Target Population: see endpoint 3
 
Treatment: See endpoint 3
 
Intercurrent Event Strategy: Intake of prohibited medication that impacts treatment effect (e.g., drug with antimalarial activity) at any timepoint: Principal Stratum strategy, i.e., treatment effect is estimated within the principal stratum of participants that potentially don't experience the ICE
 
Population-level Summary: Median time to re-emergence as estimated by Kaplan-Meier method
	15

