#### 9.4.1.2 Efficacy Analyses Related to Secondary and **CCI** Objectives

Most of the estimands targeting the secondary objectives of this study (refer to Section 3) share the attributes of the primary estimand as described in Section 9.4.1.1. Distinct attributes of each estimand are described below for each secondary endpoint.

For the secondary efficacy endpoint fever clearance time, defined as the time from first dosing to the first measurement of an axillary temperature  $< 37.5^{\circ}\text{C}$  for 2 consecutive temperature readings plus confirmed normal temperature 24 hours after the first normal body temperature reading, the target population is defined as adult and adolescent patient with acute uncomplicated malaria due to *P. falciparum* with an increased axillary temperature ( $\geq 37.5^{\circ}\text{C}$ ). For this endpoint, the composite variable strategy that is applied to handle ICEs like intake of rescue medication and intake of concomitant medications with an impact on fever (as a continuous treatment) or intake of prohibited medication that impacts the treatment effect (e.g., drug with antimalarial activity) consists of a censoring strategy. If such ICEs are observed, those patients will be censored at Day 29. Premature study discontinuation due to lack of efficacy or malaria induced death will be handled according to an on-treatment strategy, i.e., the respective patients will be censored at the day of their last available body temperature assessment. With respect to the population-level summary, the median fever clearance time will be estimated by the Kaplan-Meier method separately for the one dose and 2-day regimen treatment groups. A log-rank test will be applied to descriptively investigate differences between both treatment arms. In order to explore whether there is an impact of other covariates and factors on time to fever clearance a Cox Proportional Hazard model will be applied. Details of the models will be described in the IAP.

The same approaches as described for fever clearance time are applicable also to PCT (note that for the target population for PCT the prerequisite of showing an increased axillary temperature does not hold).

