- **Experience of any event that affects absorption (i.e., vomiting within the study intervention absorptive period of $2 \times \text{median } t_{\text{max}}$) or immune response (severe immunocompromised participants):** See Section 14.1 for description of events affecting absorption or immune response. A treatment policy strategy is applied, i.e., treatment effect is estimated regardless of intercurrent event.
- **Premature study discontinuation due to lack of efficacy:** See Section 14.1 for description of ICE. An on-treatment strategy is applied, i.e., time to fever clearance is censored at the day of the last available body temperature assessment. Note: If premature study discontinuation occurs after fever clearance has already been observed, then the strategy will not be applied.
- **Death due to malaria:** See Section 14.1 for description of death due to malaria. An on-treatment strategy is applied, i.e., time to fever clearance is censored at the day of the last available body temperature assessment. Note: If death occurs after fever clearance has already been observed, then the strategy will not be applied.

Median fever clearance time and 95% CIs will be estimated by use of the Kaplan-Meier method. Confidence intervals will be calculated using log-log transformation. Participants with no fever clearance or ICEs will be censored at the day of the last temperature assessment. Kaplan-Meier plots including a table with number of participants at risk and number of events will be provided. To explore whether there is an impact of dose group (Part A vs. Part B Cohort B0), age (continuous), sex, and parasite density at baseline on time to fever clearance, a Cox Proportional Hazards model will be applied.

[figure not shown]

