14.6 Parasite clearance time

Parasite clearance time is the duration (in days) between first dosing and the first blood draw with parasite clearance (parasite count = 0). The subsequent readings up till at least 6 hours from the first zero reading must remain zero for the presence of parasites.

[figure not shown]
The same ICEs and strategies as defined for time to fever clearance (see Section 14.5) will be applied to parasite clearance time, with the exception of intake of concomitant medications with impact on fever, which is not an ICE for parasite clearance time. Since parasite clearance time is measured in days, censoring will be done at the day of the last available microscopy assessment.

The same analysis approaches as described for fever clearance time are applicable also to parasite clearance time (note that for the target population for parasite clearance time the prerequisite of showing an increased temperature does not hold). Participants with no parasite clearance or ICEs will be censored at the day of the last microscopy assessment.

CCI

CCI

15 Safety Analyses

This section includes specifications for summarizing safety endpoints that are common across clinical studies such as adverse events, laboratory tests, and vital signs.

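### Fever and parasite clearance times censor malaria death, lack-of-efficacy discontinuation and (in the SAP) rescue early, so Kaplan-Meier overstates clearance whenever one of them precedes it

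*Protocol*

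**What the plan says.** **Protocol.** In the Synopsis (Part A, endpoint 11) and Table 3, two events in fever clearance time carry an on-treatment label and are censored at the last temperature reading: "Death due to malaria: On-treatment strategy, i.e., time to fever clearance is censored at the day of the last available body temperature assessment" and "Premature study discontinuation due to lack of efficacy: On-treatment strategy, i.e., time to fever clearance is censored at the day of the last" available reading. Section 9.4.1.2 repeats this: "Premature study discontinuation due to lack of efficacy or malaria induced death will be handled according to an on-treatment strategy". The summary is "Median fever clearance time as estimated by Kaplan-Meier method". Endpoint 12, parasite clearance time, takes these rules over by cross-reference and adds: "Censoring will be done at the day of the last available microscopy assessment". Part B endpoints 28 and 29 inherit them.

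For rescue, endpoint 11 has a different rule: "Intake of rescue medication: Composite variable strategy, i.e., time to fever clearance is censored at Day 29". Censoring at a fixed late day keeps a rescued participant in the risk set as uncleared throughout the period in which others clear.

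**SAP.** Section 14.5 keeps the rule for both events: "An on-treatment strategy is applied, i.e., time to fever clearance is censored at the day of the last available body temperature assessment". It adds that the rule is not applied when the event follows observed clearance. Section 14.6 states: "The same ICEs and strategies as defined for time to fever clearance (see Section 14.5) will be applied to parasite clearance time", leaving out only fever medication. Sections 5, 7 and 14.5 change the rescue rule: rescue within 3 days of starting treatment is now censored when it is taken. Section 14.5 also censors any other uncleared participant at the last assessment.

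For ACPR, ETF, LCF and LPF (SAP 14.1 to 14.4), malaria death, lack-of-efficacy discontinuation and rescue all count as failure.

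**The concern.** Kaplan-Meier assumes that a censored participant has the same later chance of clearing as those still uncleared and under observation. That is reasonable for someone who moves away. It is not reasonable for someone who dies of malaria, leaves because treatment failed, or needs rescue while still febrile or parasitaemic. Such a person is removed because of the outcome being measured. The result describes clearance as if the failure had not happened, which the on-treatment label does not convey. A malaria death is analysed exactly like an administrative dropout.

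The error runs one way: failures leave the denominator and their weight passes to those who clear. SAP section 7 records that Cohorts B1 to B3 were not enrolled, so there is no concurrent control with the same error. The same censored times enter the Cox model in SAP 14.5, which includes Part A versus Cohort B0 as a factor. No competing-risk or sensitivity analysis for these events appears in the text available.

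**Working it through.** The plan gives no numerical expectation for either clearance time, so there is no stated figure to reproduce.

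**Direction.** At a clearance time with *d* clearances, let *r* be the number at risk if failures are held as uncleared, and *c* the number of failures already censored. The survival factor is 1 − d/(r − c) as written and 1 − d/r if held. The first is never larger. The uncleared curve as written therefore lies on or below the held curve at every time: the proportion cleared can only be higher and the median only shorter.

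**Inputs from the documents.** Planned sizes are 12 (Part A) and 25 (Cohort B0). Blood films are taken every 6 hours to 72 h, and Day 29 is 28 × 24 = 672 h. The fever analysis includes only participants with a raised temperature, so its numbers may be smaller and one event may weigh more.

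**Assumptions.** *k* participants fail and never clear. The others clear evenly over the 6-hourly grid from 12 to 72 h. Failures have their last reading at 12, 24 or 48 h. The median is the first time the uncleared proportion is at or below 0.5.

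**One case in full: n = 12, k = 1, last reading at 24 h.**

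- Clearances at 12, 18 and 24 h: 11/12 × 10/11 × 9/10 = 0.75 uncleared under both rules.
- As written, 12 − 3 − 1 = 8 remain at risk and all 8 clear. Uncleared is 0.75 × 6/8 = 0.563 at 36 h, 0.75 × 5/8 = 0.469 at 42 h, and 0.75 × 0/8 = 0 at 72 h. The median is 42 h and the final proportion cleared is 100%.
- Held to Day 29, uncleared is 6/12 = 0.5 at 42 h and 1/12 = 0.083 at 72 h. The median is 42 h and the final proportion cleared is 91.7%.

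**All cases** (as written / held to Day 29):

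| n | k | Final % cleared | Median (h), last reading at 12 or 24 h | Median (h), last reading at 48 h |
|---|---|---|---|---|
| 12 | 1 | 100 / 91.7 | 42 / 42 | 42 / 42 |
| 12 | 2 | 100 / 83.3 | 42 / 42 | 42 / 42 |
| 12 | 3 | 100 / 75.0 | 36 / 48 | 48 / 48 |
| 12 | 5 | 100 / 58.3 | 36 / 54 | 54 / 54 |
| 25 | 1 | 100 / 96.0 | 42 / 42 | 42 / 42 |
| 25 | 4 | 100 / 84.0 | 42 / 48 | 48 / 48 |
| 25 | 10 | 100 / 60.0 | 42 / 60 | 54 / 60 |

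The held figure is (n − k)/n. As written, the curve reaches 100% for any *k*, provided the last person under observation clears. The medians depend a little on convention: in the worked case the held curve stands at exactly 0.5 from 42 to 48 h, and averaging the two ends would give 45 h.

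**The case against.** The strongest reply is that the rule will rarely matter. Participants are in hospital for 72 h with six-hourly films. Protocol 6.8.1 and 7.1 tie early failure to rescue, so most failures would meet the rescue rule first. Stopping study intervention does not by itself end follow-up (Protocol 7.1), although 6.8.1 also allows withdrawal together with rescue. The endpoints are secondary and descriptive, and SAP section 7 drops the between-arm tests. The failures are not concealed either, since the same events count against the drug in ACPR, ETF, LCF and LPF. The reported summary is the median, which one or two events usually leave unchanged.

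This stands as a limit on size. It does not defend the rule. The plotted curve is wrong after a single event, and sending most failures through the rescue rule is no protection once the SAP censors rescue at intake.

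Three stronger readings are tempting but not supported:

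- **That up to 40% of Part A would be affected and the median shifted by many hours.** The 2.5% to 40% in Protocol 2.3.1 is a predicted early-treatment-failure rate (0.3 to 4.8 of 12 participants). It is not a rate of malaria death, withdrawal or rescue before clearance, and serves only as an outer bound on failures.
- **That the analysis to be run treats rescue and death in opposite ways.** That contrast exists in the protocol. In the SAP both are censored early.
- **That the SAP has switched off all intercurrent-event rules for fever clearance.** The sentence saying that strategies will not apply sits, in 14.5, with fever medication taken before dosing. Even on a wider reading, uncleared participants are still censored at their last temperature reading.

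**Conclusion.** The point holds for the SAP as it stands. Malaria death, lack-of-efficacy discontinuation and rescue within 3 days, when they come before observed clearance, are censored because treatment failed. The estimated proportion cleared is then too high, and the median is either unchanged or too short.

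One event moves the final estimate from 91.7% (n = 12) or 96% (n = 25) to 100%, assuming that the failure would not have cleared and that everyone else does. The median shifts by 6 to 18 h only with several early failures (3 to 5 of 12, or 4 to 10 of 25, last reading by 24 h), and the documents give no reason to expect that many. With no such event, the results are identical. The effect is confined to secondary, descriptive endpoints. It is still worth correcting, because the rule contradicts how the plan classifies the same events elsewhere and can only err in the drug's favour.

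**What to change.** Amend SAP section 5 (endpoints 11, 12, 28 and 29), 14.5 and 14.6, and record the change in section 7:

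1. If malaria death, discontinuation for lack of efficacy, or rescue occurs before clearance has been observed, the participant stays in the risk set as uncleared and is censored at Day 29. For rescue this restores the protocol's rule, so the corresponding change in SAP section 7 should be withdrawn for rescue. The protocol rule has no 3-day limit; the test should be whether clearance came first.
2. This rule takes precedence when a participant has more than one event. Without that sentence, changing only death and discontinuation would leave someone who is rescued and then withdrawn under two opposite rules.
3. Keep the exception for events after observed clearance.
4. Keep censoring at the last reading for losses unrelated to efficacy. In 14.6, limit the sentence on the last microscopy day to those losses so that it does not override point 1.

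The cost is a few SAP sentences, no new data, and a slightly less favourable estimate if such events occurred. Revising the protocol would add little, since only Part A and Cohort B0 will be analysed.
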